9.9 Subgroup analyses

Subgroup analyses will be performed by gender and documented history of prior COVID-19 infection (yes/no), respectively.

As the sample size was fixed for part B overall, but not for the individual cohorts, the observed sample sizes in the cohorts might differ substantially. Therefore, cohorts might be merged based on the final sample sizes observed and scientific reasoning.

Only for a subgroup of subjects certain endpoints as defined in the trial protocol (see variables in first column of the visit schedule marked with subindex c) will be determined. Currently, in a first step this will include the first 200 enrolled subjects across Part A und B, but may be expanded later if additional funding becomes available.

9.10 Interim Analysis

An interim analysis will be performed as soon as 50% of participants have been recruited within Part B. In the interim analysis, Haybittle–Peto boundaries of 0.0001 will be used to calculate the confidence intervals for the primary analysis in each cohort. There will be no stopping because of differences in the primary endpoint analysis at interim analysis..

If a treatment arm is dropped due to safety concerns, a sample size re-allocation to the remaining arms might be considered. However, in this case the overall sample is still fixed as initially planned, i.e., the total sample size over all cohorts in Part B is bounded by 550 patients in total

The interim analysis will allow for a sample size reassessment in the interim analysis, e.g., to re-estimate the standard deviation. If a sample size reassessment is performed, the conditional error principle is implemented to control the FWER for the primary endpoint.

Note: In case enrolment is much faster than assumed at the time of trial design, the interim analysis may be omitted.

10 Safety Analysis

Summaries and analysis of safety data will be presented for the Safety Analysis Population.

An adverse event (AE) is any untoward medical occurrence in a trial subject administered an IMP. There does not necessarily have to be a causal relationship with this treatment. The adverse event may be, but is not restricted to: a new illness, worsening of a sign or symptom following trial-specific treatment (here 4th vaccination dose), the clinically significant abnormal results of an examination (e.g., laboratory findings, electrocardiogram) or deterioration of a pre-existing medical condition, or a combination of two or more of these factors, as applicable.

AEs will be documented starting from baseline visit and until the last scheduled visit after the 4th vaccine dose unless otherwise defined in the sub-protocol specific visit schedule.

The safety endpoints includes

- Unsolicited AEs until the end of trial.
- Solicited AEs for 7 days after a 4th vaccination dose.
- Rate of serious adverse events (SAEs) Grade ≥ 3 according to the National Cancer Institute Common Toxicity Criteria up to three months after a 4th vaccination dose.

Listing will be provided on a subject level reporting the severity and relationship to study vaccination (related / unrelated). Absolute and numbers in percent will be given per intervention group.

Different types of AEs will be grouped. Additionally the safety data will be reported descriptively for each intervention and cohort separately.

11 Software program(s):

All statistical analyses will be conducted with statistical software like SAS 9.4. (or higher) and R 3.6.3. (or higher).

12 Sample size calculation

The number needed has been calculated at 550 for part B (i.e., 600 overall for Part A and B, and including a potential dropout rate of 8-10% for Part B).

12.1 Sample size calculation with multiplicity adjustment:

Sample size calculation has been carried out for the primary endpoint for the rate π of 2-fold antibody titre increase following 4th dose vaccination. As two-sided simultaneous 95% confidence intervals for this rate should be calculated separately for each randomized group in Part B a Bonferroni adjustment was used in the sample size calculation accordingly.

When the sample size is 250 per randomized group, two-sided simultaneous 95% confidence intervals (with Bonferroni adjustment for 2 simultaneous confidence intervals in a cohort) for a proportion using the large sample normal approximation will extend no more than $\pm 7.1\%$ (percentage points) from the observed proportion. E.g., if the observed proportion is 50% (where the confidence interval is widest), the confidence interval ranges from about 42.9% to 57.1%.

To adjust for potential dropouts in part B of about 8-10%, the total sample size for part B (=4th vaccination and Cohorts 4-9) was set to 550.

In the table below the precision for the simultaneous two-sided 95%-confidence intervals (with the same assumptions as described above) is shown for varying sample sizes. This shows which precision could be achieved in the different cohorts based on the previous vaccination strategy (see also inclusion criteria for Part B).

Sample Size, n	250	200	150	125	90	50	40
Expected Proportion, π	0.500	0.500	0.500	0.500	0.5	0.500	0.5
Distance from Proportion to Limit, ω	0.071	0.079	0.092	0.100	0.118	0.158	0.177

Also, the sample size of n=550 in part B shall provide adequate power for comparison in GMT (Geometric mean titre values) between the two randomised treatment arms in aged patients, e.g., comparison of different boosting strategies depending on the initial vaccination. E.g., demonstration of equivalent immune response after heterologous boosting, in comparison with the homologous approach, will facilitate vaccination programs when vaccine availability is an issue.

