With a booster dose of mRNA-1273 identical to the doses of the primary vaccination series very old individuals (> 75 years) with assumed immunosenescence²⁹ may thus benefit from increased immunogenicity while not being exposed to a currently detectable increased risk of myocarditis/pericarditis.

Meanwhile, Moderna Tx. has communicated data that demonstrate markedly increased levels of Omicron neutralizing antibodies after the 100 µg mRNA-1271 booster (3rd) dose as compared to the 50 µg dose³⁰.

A full booster (3rd) dose (0.5 ml, 100 µg) of mRNA-1273 was administered in two subgroups of the COV-BOOST trial, either following primary vaccination series with twice ChAdOx1-S or twice BNT162b2. The median age in the ChAdOx1-S subgroup (n=112) was 70.2 years and 65.0 years in the BNT162b2 group (n=111)³¹. Data on a full dose mRNA-1273 booster in the very old above 75 years of age is thus still missing.

4.7.7. Time of administration and adjustments to dosage of the investigational medicinal product in the individual trial subject

Not applicable.

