4.9.1. Rationale for assessment procedures

Monitoring of immunogenicity at 14 days has been a standard time-point for COVID-19 vaccines and the immunogenicity test performed at 3, 6 and 12 months are considered adequate for evaluating the duration of immunity in this population vaccinated against COVID-19.

Subjects will be evaluated for reactogenicity events during the first 14 days after 4th dose administration (solicited AEs until Day 7; unsolicited AEs up to Day 14 and until the end of trial) and thereafter every 3 months after 4th vaccination dose according to visit schedule (see Table 3) for SAEs reported. This is considered sufficient for safety monitoring of already marketed vaccines.

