7.1.6. Adverse events of special interest

According to section 7.1.6. in the accompanying master protocol:

An adverse event of special interest (AESI) is an adverse event that may not be serious but has special meaning or importance for the clinical trial. AESI will be recorded if considered described specifically in a sub-protocol under the master protocol.

Specific to this trial:

No AESI are considered in this trial, besides solicited adverse events.

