Statistician	Assoc. [name].-Doz. [name] [name] Center for Medical Statistics, Informatics and Intelligent Systems Medical University of Vienna [name], [name] Austria														
Statistical methods (Part B)	
Firstly, the rates of 2-fold increase in antibody titre with multiplicity adjusted 95% confidence intervals (adjusted for arms within each cohort) will be reported for both randomized groups 1 and 2 in Part B.
 
Secondly, Cohorts of study participants are defined by the different pre-vaccination series eligible for part B of this trial. We compare the 4th vaccination doses of BNT162b2 and mRNA-1273 and compute a two-sided confidence interval. Based on these we test for equivalence of one of the 4th vaccination doses (based on the equivalence margin as outlined in the Reflection Paper of EMA).
														

	
Thirdly, we compare groups 1 and 2 based on homologous boosting (pre-study 3rd vaccine and on-study 4th vaccine identical) vs. heterologous boosting (pre-study 3rd vaccine and on-study 4th vaccine different). Further exploratory analyses will be performed based on different pre-vaccination series.
 
The primary endpoint analysis in part B will be performed as soon as single cohorts have completed day 14 of the visit schedule. The primary endpoint analysis will be triggered as soon as for all patients the primary endpoint (14 days after the 4th vaccination dose) has been observed.
 
Safety analysis.
 
All clinical safety data will be listed by participant, time from vaccination dose and treatment arm. Continuous variables will be summarised using sample size (N), mean, standard deviation, median, minimum, and maximum. Frequency counts will be reported for categorical data. A Data and Safety Monitoring Committee (DSMC) will review data for decisions on arms incorporation and withdrawal and will ensure the appropriate oversight and monitoring in conducting the clinical trial.
 
Interim analysis
 
An interim analysis will be performed as soon as 50% of participants have been recruited within Part B.

GCP compliance	The present trial will be conducted in accordance with the valid versions of the trial protocol and the internationally recognised Good Clinical Practice Guidelines (ICH-GCP), including archiving of essential documents.
Financing	European Commission

1 Objectives of the clinical trial

Primary objective (Part B)

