9.1 Analysis populations

According to section 6.1.1 in the accompanying master protocol:

The primary dataset for analysis is derived from the intention-to-treat (ITT; Full Analysis Set, FAS) population. This dataset includes all trial subjects enrolled into the trial and randomised.

The evaluation is carried out strictly in accordance with the allocation by randomisation.

The secondary dataset for analysis is derived from the per-protocol (PP) population. This dataset includes all trial subjects who were treated according to protocol and reached a defined endpoint in the trial.

The tertiary dataset for analysis is the safety population. This population includes all trial subjects who received any IMP or other trial treatment.

Specific to this trial:

All analysis population defined here are specific for part B (using subjects from part B only).

Modified intention-to-treat population (mITT) Population.

The mITT population includes all subjects who received a study vaccine (as randomised and administered accordingly) and contributed both pre- and at least one post-vaccination blood sample for immunogenicity testing for which valid results were reported.

Primary Analysis Population

The primary analysis population is a subset of the modified intention-to-treat population (mITT), consisting of all randomised subjects whose primary endpoint measurement is

available. Please note the primary analysis population will include subjects with an anti-Nucleocapsid IgG at visit 2 indicative of SARS-CoV-2 infection.

Per Protocol Population

In the final analysis, protocol deviations will be reviewed to determine which protocol deviations may affect the analysis. The per protocol (PP) population includes all subjects in the mITT subset, but will exclude the following subjects:

- Data from all visits from subjects found to be ineligible at baseline
- Patients who have had a known new SARS infection between baseline and the visit concerned.
- Data from all visits subsequent to major protocol deviations that are considered to affect the outcome
- Data from any visits that occurred substantially out of the foreseen time window

Safety Population

The population for the safety analysis will be all randomised subjects that received a study vaccine. Analyses for the safety population will include safety reported through the end of the study.

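### Day 14 is named for unsolicited AEs, but SAP 10 summarises them by arm only to the end of trial; a day 0–14 table would be a free improvement

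*SAP*

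**What the plan says.** SAP section 10 and protocol 6.2 list three safety endpoints, each with its own period: solicited AEs for 7 days, Grade 3 or higher events for three months, and "Unsolicited AEs until the end of trial". For the summary, "Absolute and numbers in percent will be given per intervention group", with a further descriptive breakdown by intervention and cohort, and "Different types of AEs will be grouped". On the safety population, SAP 9.1 adds: "Analyses for the safety population will include safety reported through the end of the study". Follow-up lasts 12 months after the dose (SAP 8).

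Day 14 does appear. SAP 7 and protocol 4.8 carry over a master-protocol sentence that names unsolicited and solicited AEs at day 14 as safety variables of interest, where applicable. Protocol 4.9.1, specific to this trial's visits, describes "unsolicited AEs up to Day 14 and until the end of trial". Neither becomes a table in SAP 10.

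Time since the dose is kept in the listings. The SAP synopsis (Statistical methods, Part B) says: "All clinical safety data will be listed by participant, time from vaccination dose and treatment arm". Protocol 7.2.1 has the date and time of onset of each AE entered in the eCRF. Protocol 7.1.6 says: "No AESI are considered in this trial, besides solicited adverse events".

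**The concern.** A vaccine effect on tolerability is expected mainly in the first days or weeks. Over a year, many people aged 75 or older will have some unrelated illness. If both are counted in one percentage per arm, a participant who would have had an unrelated event anyway no longer contributes to the early contrast, so the difference shrinks and the comparison becomes less precise.

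Two other endpoints cover part of the early period by arm: the 7-day diary and the three-month Grade 3 or higher rate. That leaves Grade 1–2 events that are off the diary list or that start on days 8–14. Lymphadenopathy and acute facial paralysis, for example, are among the reported side effects in protocol 4.3.1 but are not in the solicited list in protocol 7.1.7. With no AESI beyond the solicited events, lower-grade events of this kind are counted only as unsolicited AEs.

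The early comparison matters because of a stated evidence gap. On the 100 µg dose, protocol 4.7.6.1 says: "Data on a full dose mRNA-1273 booster in the very old above 75 years of age is thus still missing".

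**Working it through.** **The plan's own figure.** The documents give no AE rate and no precision figure for AEs. The only sizing figure is for the primary endpoint: with 250 per group, 2.2414 × √(0.25/250) = 0.0709, which reproduces the stated ±7.1 points. It says nothing about AEs. The arm size used below is 550/2 = 275.

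**Inputs from the documents.** Follow-up is 12 months and the early period is 14 days, so days 0–14 make up 14/365 = 3.8% of the window.

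**Assumptions.**
- The 12-month background risk B is equal in both arms, accrues at a constant rate and is independent of the early vaccine-related risk e.
- All early vaccine-related events fall within days 0–14.
- B is varied from 1% to 60%.

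**Formula.** With background risk b in a window, the proportion with at least one event is 1 − (1−b)(1−e). The between-arm difference is (1−b)(e₂−e₁), so the share of the early difference that is kept is 1−b, whatever e₁ and e₂ are. Over 12 months, b = B. Over days 0–14, b = 1 − (1−B)^(14/365).

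| B (assumed) | Kept over 12 months | b, days 0–14 | Kept, days 0–14 |
|---|---|---|---|
| 60% | 40% | 0.0345 | 97% |
| 40% | 60% | 0.0194 | 98% |
| 20% | 80% | 0.0085 | 99% |
| 10% | 90% | 0.0040 | 99.6% |
| 5% | 95% | 0.0020 | 99.8% |
| 1% | 99% | 0.0004 | about 100% |

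**Background cases per arm of 275.** At B=60%: 0.60 × 275 = 165 over 12 months, against 0.03453 × 275 = 9.5 in days 0–14. At B=10%: 27.5 against 1.1.

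**Illustration of precision.** Assume early risks of 5% and 10%. The 95% half-width is 1.96 × √[p₁(1−p₁)/275 + p₂(1−p₂)/275].

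- B=60%, 12 months: p₁ = 1 − 0.4×0.95 = 0.62 and p₂ = 1 − 0.4×0.90 = 0.64; difference 2.0 points, half-width 8.1.
- B=60%, days 0–14: p₁ = 1 − 0.9655×0.95 = 0.083 and p₂ = 1 − 0.9655×0.90 = 0.131; difference 4.8 points, half-width 5.2.
- B=10%, 12 months: 14.5% v 19.0%; difference 4.5 points, half-width 6.2.
- B=10%, days 0–14: 5.4% v 10.4%; difference 5.0 points, half-width 4.5.

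**Which rows apply.** The upper rows describe one pooled percentage for any unsolicited AE. The lower rows describe a single uncommon AE type, or a count limited to related events.

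**The case against.** The strongest reply is that this is table layout. SAP 10 does not say there will be only one table over one window, and SAP 9.1 settles which data enter the analysis, not how tables are cut. Day 14 is already named in SAP 7 and in protocol 4.8 and 4.9.1, so a reader who inferred that the plan overlooks an early period would be wrong. That stands as a limit on the point. But the SAP 7 and protocol 4.8 sentence is inherited and conditional, and the trial-specific endpoint and SAP 10 name no early by-arm summary.

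A second reply is that the large losses need a pooled proportion and a high background. This also stands. AE types will be grouped, so it would be wrong to infer that a signal for facial paralysis or lymphadenopathy would be largely hidden: at B of 5% to 1%, 95–99% of the difference is kept. No value of B can be drawn from the documents, and the 5% v 10% contrast is only an illustration.

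Third, a reader might infer that early safety goes unexamined or that information is lost. The documents do not support that. The diary and the Grade 3 or higher rate cover much of the acute period, listings show time from dose, and onset dates allow a later cut. What the listings do not give is a by-arm rate. The trial is also open-label and SAP 9 plans no blind data review, so a window fixed beforehand is more convincing than one chosen afterwards.

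Finally, SAP 7 counts only related events among unsolicited AEs that the participant grades severe, while protocol 7.2.1 documents all AEs. Which of these the tables count is a separate wording question, and this point does not rest on it.

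**Conclusion.** The point holds in a narrow form. The documents name day 14 for unsolicited AEs, but the by-arm summary actually specified runs to the end of trial. For a pooled percentage of any unsolicited AE, that keeps 40% of an early difference at an assumed 12-month background of 60%, and 80% at 20%, against about 97% and 99% in a day 0–14 table. For single rare types or related-only counts the loss is minor. These figures rest on equal, constant and independent background risk and on all early vaccine-related events falling within 14 days.

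The affected events are Grade 1–2 events off the diary list or starting on days 8–14. The split would not guarantee detection: in the B=60% illustration, 4.8 points with a half-width of 5.2 still includes zero. It is an optional improvement with a modest benefit, and it serves the trial's safety objective at almost no cost.

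**What to change.** Add one sentence to SAP section 10:

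> Unsolicited AEs with onset on days 0–14 and from day 15 to end of trial will be tabulated separately by intervention group, overall and by AE type, as n (%).

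The tables are descriptive, with no test and no effect on multiplicity. They use onset dates already collected in the eCRF. The cost is that sentence and a few extra tables: no protocol change, no new data, no added visits and no added participants.

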	APPENDIX A: Statistical Analysis Plan for part A
Title of Trial	A Multinational, Phase 2, Randomised, Adaptive Protocol to Evaluate Immunogenicity and Reactogenicity of Different COVID-19 Vaccines Administration in Older Adults (≥ 75) Already Vaccinated Against SARS- CoV-2 (EU-COVAT-1 Aged)
Short Title	EU-COVAT-1 Aged
Sponsor Trial No.	uni-koeln-4602
EudraCT No..	2021-004526-29

PLEASE NOTE:

The APPENDIX A of this SAP refers to Part A.

Part A of the present trial in which individuals received a 3rd vaccination (first booster) was closed to further recruitment as of January 13, 2022. With the massive roll-out of booster campaigns throughout Europe, Part A was abandoned because of a poor recruitment rate.

Individuals in Part A are followed-up as specified in protocol version V04_0. Therefore, the overview on part A and any references in appendix A to parts in the study protocol refer protocol version V04_0 (which covers Part A).

Sponsor	University of Cologne Represented by: [name]. med. [name] (Principal Coordinating Investigator, PCI) Department for Internal Medicine I University Hospital Cologne [name] [name] Germany
Principal Coordinating Investigator	See above National representatives are detailed in a separate list for this multinational trial.
Title of the clinical trial	A Multinational, Phase 2, Randomised, Adaptive Protocol to Evaluate Immunogenicity and Reactogenicity of Different COVID-19 Vaccines Administration in Older Adults (≥ 75) Already Vaccinated Against SARS-CoV-2 (EU-COVAT-1 Aged)
Indication	COVID-19 vaccination
Phase	Phase II clinical trial

Type of trial, trial design, methodology	
Please note: This trial (“EU-COVAT-1_Aged”) is a sub-protocol embedded within the EU-COVAT master protocol.
 
This is a randomised controlled, adaptive, multicentre Phase II protocol evaluating different booster strategies in individuals aged 75 years and older already vaccinated against SARS-CoV-2. This trial foresees testing of different vaccines as a third/booster dose for comparative assessment of their immunogenicity and safety against SARS-CoV-2 and SARS-CoV-2 variants in the elderly, a usually neglected population. Different vaccines and extended follow-up visits can be added through amendments of this sub-protocol. As stated in the EU-COVAT master protocol, this trial, i.e., the EU-COVAT-1 Aged study, implements a specific safety monitoring strategy (see below).
 
Randomisation
 
Subjects will be randomised to one of the arms planned in an equal allocation ratio. The allocation ratio is in each of the three cohorts 1:1 to the two arms BNT162b2 (Comirnaty) and mRNA-1273 (Spikevax).
 
Cohorts and arms can be withdrawn or added as deemed necessary according to the criteria specified in this protocol.
 
Blinding
 
No blinding is foreseen in this trial

Number of subjects	
The number needed has been calculated at 100 subjects per arm (i.e., 600 in total, including an assumed 10% of dropouts, for the 6 planned initial arms).
 
Sample size calculation with multiplicity adjustment within each cohort
 
When the sample size is 90 per group (without dropouts, i.e., 100 including 10% dropouts), two-sided simultaneous 95% confidence intervals (with Bonferroni adjustment for 2 simultaneous confidence intervals within a cohort) for a proportion using the large sample normal approximation will extend no more than $\pm 12\%$ (percentage points) from the observed proportion. E.g., if the observed proportion is 50% (where the confidence interval is widest), the confidence interval ranges from about 38% to 62%.

Primary trial objective	
To evaluate immune response against wild-type SARS-CoV-2 of different booster strategies in elderly subjects (≥ 75 years old) already fully vaccinated against SARS-CoV-2.

Secondary trial objectives	
 • To compare the humoral immune response against wild-type SARS-CoV-2 between treatment arms within each cohort following 3rd vaccination dose in elderly individuals (≥75 years) already vaccinated against SARS-CoV-2. • To compare the humoral immune response against wild-type SARS-CoV-2 between cohorts following 3rd vaccination dose in elderly individuals (≥75 years) already vaccinated against SARS-CoV-2. • To evaluate immune response against SARS-CoV-2 variants of concern of different booster strategies in elderly individuals (≥75 years) already fully vaccinated against SARS-CoV-2. • To assess the CD4+ and CD8+ T cell response of different booster strategies in elderly individuals (≥75 years) already vaccinated against SARS-CoV-2. • To evaluate the long-term humoral immune response of different booster strategies in individuals already fully vaccinated against SARS-CoV-2.
Safety objectives	
 • To assess the safety of different booster strategies in elderly individuals (≥75 years) already vaccinated against SARS-CoV-2.

Study end points	
Primary end point:
 
 • Rate of 2-fold antibody titre increase following 3rd dose vaccination measured by quantitative enzyme-linked immunosorbent assay (Anti-RBD-ELISA) against wildtype virus 14 days after 3rd dose. 
Secondary end points:
 
Safety:
 
 • Unsolicited AEs until the end of trial. • Solicited AEs for 7 days after 3rd dose. • Rate of serious adverse events (SAEs) Grade ≥3 according to the National Cancer Institute Common Toxicity Criteria up to three months after 3rd dose. 
Immunogenicity:
 
 • Antibody titre increase following 3rd dose measured by neutralising activity against wildtype virus (Virus Neutralisation Assay) in a subgroup 14 days after 3rd dose. 
Immunogenicity against variants:
 
 • Change in neutralising capacity measured by neutralising activity against variants of concern (Virus Neutralisation Assay) in a subgroup 14 days after 3rd dose. 
Long-term immunity:
 
 • Antibody titre level following 3rd dose measured by a quantitative enzyme-linked immunosorbent assay (anti-RBD-ELISA assay) 12 months after 3rd dose. • Antibody titre level following 3rd dose measured by neutralising activity against wildtype virus (Virus Neutralisation Assay) in a subgroup 12 months after 3rd dose. • Change in neutralising capacity 12 months after 3rd dose measured by neutralising activity against variants of concern (Virus Neutralisation Assay) in a subgroup of subjects. 
Exploratory endpoints:
 
 • Change in cellular immune response measured by qPCR 14 days after 3rd dose in a subgroup analysis. • Neutralising capacity measured by neutralising activity against newly emerging variants in bio-banked samples in a subgroup analysis.
-------------------------	--

	
 • Correlates of humoral immune response, cellular immune responses and viral neutralising capacity against SARS-CoV-2 variants of concern (VOCs).
Diagnosis and Principal inclusion and exclusion criteria	
Medical condition or disease to be investigated: Prevention of COVID-19 infection.
 
Principal inclusion criteria:
 
 • Elderly (≥ 75 years old). • Already fully vaccinated adults. • Primary vaccination (1st and 2nd dose) using BNT162b2, mRNA-1273 or ChAdOx-1-S). • No contra-indication against any of the vaccine products in the trial at time of enrolment. 
Stratification and subpopulations:
 
 • Vaccine product used for primary vaccination (homologous 1st and 2nd dose using BNT162b2, mRNA-1273 or ChAdOx-1-S). • Gender. • Documented history of prior COVID-19 infection (if more than 3 months ago prior to enrolment; yes/no). 
Principal exclusion criteria:
 
 • Primary vaccination performed with different vaccine products as sole (e.g., COVID-19 Vaccine Janssen) or, 1st and 2nd vaccination doses (heterologous vaccination scheme). • Any contraindication against any of the vaccines at time of enrolment including current SARS-CoV-2 infection or proven in the last 3 months. • Immunocompromised status.
Name of investigational medicinal product (IMP)	
 • BNT162b2 (Tradename Comirnaty) • mRNA-1273 (Tradename Spikevax)

Investigational medicinal product – dosage and method of administration	
Intervention: mRNA-based booster strategies following different prime boost vaccination strategies.
 
  
 Cohort	Prime strategy	Intervention Arm	Intervention: Third dose	Interval	
   
 Cohort 1	BNT162b2 - BNT162b2	1	BNT162b2	9 ± 3 months from date of 2nd vaccine dose upon enrolment	
 
 2	mRNA-1273	
 
 Cohort 2	mRNA-1273 - mRNA-1273	3	BNT162b2	
 
 4	mRNA-1273	
 
 Cohort 3	ChAdOx-1-S - ChAdOx-1-S	5	BNT162b2	
 
 6	mRNA-1273	
 
 Control		Control arm of the EU-COVAT subprotocol EudraCT no. 2021-004889-35, a separate sub-protocol embedded within the EU-COVAT master protocol*	
  
 
*The control arm will be used for a descriptive comparison.
	Cohort	Prime strategy	Intervention Arm	Intervention: Third dose	Interval	Cohort 1	BNT162b2 - BNT162b2	1	BNT162b2	9 ± 3 months from date of 2 nd vaccine dose upon enrolment	2	mRNA-1273	Cohort 2	mRNA-1273 - mRNA-1273	3	BNT162b2	4	mRNA-1273	Cohort 3	ChAdOx-1-S - ChAdOx-1-S	5	BNT162b2	6	mRNA-1273	Control		Control arm of the EU-COVAT subprotocol EudraCT no. 2021-004889-35, a separate sub-protocol embedded within the EU-COVAT master protocol*		
Cohort	Prime strategy	Intervention Arm	Intervention: Third dose	Interval																										
Cohort 1	BNT162b2 - BNT162b2	1	BNT162b2	9 ± 3 months from date of 2 nd vaccine dose upon enrolment																										
		2	mRNA-1273																											
Cohort 2	mRNA-1273 - mRNA-1273	3	BNT162b2																											
		4	mRNA-1273																											
Cohort 3	ChAdOx-1-S - ChAdOx-1-S	5	BNT162b2																											
		6	mRNA-1273																											
Control		Control arm of the EU-COVAT subprotocol EudraCT no. 2021-004889-35, a separate sub-protocol embedded within the EU-COVAT master protocol*																												
IMP or therapy used as a comparator – dosage and method of administration	No vaccination in the control group of the EU-COVAT subprotocol EudraCT no. 2021-004889-35, a separate sub-protocol embedded within the EU-COVAT master protocol																													
Duration of treatment:	Treatment consists of a single 3 rd boost dose of each vaccine included in this protocol. Follow up of subject included will last for 12 months after boost dose.																													
Time plan	
 
 First patient first visit (FPFV):	October 2021	
 
 Last patient first visit (LPFV):	March 2022	
 
 Last patient last visit (LPLV):	April 2023	
 
 Analysis	April 2022 (Primary endpoint analysis)	
 
 End of study definition	The end of study will be on the day of database lock.	
 
 End of trial	May 2023	
 
 Final study report:	July 2023	
 
	First patient first visit (FPFV):	October 2021	Last patient first visit (LPFV):	March 2022	Last patient last visit (LPLV):	April 2023	Analysis	April 2022 (Primary endpoint analysis)	End of study definition	The end of study will be on the day of database lock.	End of trial	May 2023	Final study report:	July 2023															
First patient first visit (FPFV):	October 2021																													
Last patient first visit (LPFV):	March 2022																													
Last patient last visit (LPLV):	April 2023																													
Analysis	April 2022 (Primary endpoint analysis)																													
End of study definition	The end of study will be on the day of database lock.																													
End of trial	May 2023																													
Final study report:	July 2023																													

Statistician	
Assoc. [name].-Doz. [name] [name] Center for Medical Statistics, Informatics and Intelligent Systems Medical University of Vienna [name], [name] Austria

Statistical methods	
Firstly, the rates of 2-fold increase in antibody titre with simultaneous 95% confidence intervals (adjusted for the 6 comparisons) will be computed.
 
Secondly, each of the three prime strategies (BB, MM, AA) define a cohort of study participants. For each cohort, we compare the boosters B and M and compute a two-sided confidence interval. Based on these we test for equivalence of one of the 3rd vaccination dose (based on the equivalence margin as outlined in the Reflection Paper of EMA).
 
Thirdly, the heterologous prime-boost COVID-19 vaccination will be assessed for equivalence in humoral immune response against VOC compared to approved homologous COVID-19 vaccination.
 
The primary endpoint analysis will be performed as soon as single cohorts have completed day 14 of the visit schedule. The primary endpoint analysis will be triggered as soon as for all patients the primary endpoint (14 days after 3rd vaccination) has been observed.
 
Safety analysis.
 
All clinical safety data will be listed by participant, time from vaccination dose and treatment arm. Continuous variables will be summarised using sample size (N), mean, standard deviation, median, minimum, and maximum. Frequency counts will be reported for categorical data.
 
A Data and Safety Monitoring Committee (DSMC) will review data for decisions on arms incorporation and withdrawal and will ensure the appropriate oversight and monitoring in conducting the clinical trial. An interim analysis will be implemented if deemed necessary, when 300 participants completed the primary endpoint assessment.

GCP compliance	The present trial will be conducted in accordance with the valid versions of the trial protocol and the internationally recognised Good Clinical Practice Guidelines (ICH-GCP), including archiving of essential documents.
Financing	European Commission

13 General aspects of trial design

According to section 4.1 of the accompanying master protocol:

This is a randomised, adaptive, multicentre, Phase II master protocol evaluating different booster strategies in individuals already vaccinated against SARS-CoV-2. This protocol allows testing of different booster strategies to assess their immunogenicity and safety against SARS-CoV-2 and its variants. Different trial populations, different vaccines, additional doses and vaccination time points, and extended follow-up visits can be added throughout amendments of the master protocol. The master protocol contains a common control group that does not receive a 3rd vaccination dose. This control group is used for exploratory comparison as applicable. The trial implements a specific safety monitoring strategy for this control group.

13.1 Specific to this trial:

This is a randomised controlled, adaptive, multicentre Phase II protocol evaluating the immunogenicity and reactogenicity of different booster strategies in individuals ≥ 75 years already vaccinated against SARS-CoV-2. This trial foresees testing of different vaccines as booster/3rd dose to assess their immunogenicity and safety against SARS-CoV-2 and SARS-CoV-2 variants in aged population, a usually neglected population. Different vaccines and extended follow-up visits can be added by means of amendments to this sub-protocol. As stated in the master protocol, this trial implements a specific safety monitoring strategy for the control group (see below).

Subjects in each cohort will be randomised to one of the arms planned in an equal allocation ratio. In each cohort, the arms foreseen at this moment are 2; therefore, the allocation ratio within in each cohort will be 1:1.

Arms can be withdrawn or added as deemed necessary according to the criteria specified in this protocol.

Figure 1 shows a schematic flow chart of the trial design planned for part A.

[figure not shown]

Figure 2: Flow chart of the trial design

Legend: A = Astra Zeneca vaccine ChAdOx-1-S, B = BioNTech vaccine Comirnaty, M = Moderna vaccine Spikevax; D14 = day 14, M3/6/12 = month 3/6/12

14 Discussion of trial design

According to section 4.2 of the accompanying master protocol:

Trials under the master protocol allow testing of different booster strategies to assess their immunogenicity and safety against SARS-CoV-2 and its variants. Different trial populations, different vaccines, additional doses and vaccination time points, and extended follow-up visits can be added throughout amendments of the master protocol or trials under the master protocol.

Specific to this trial:

This trial is a sub-protocol embedded within the master protocol EU-COVAT: A Randomised, Controlled, Adaptive, Multicentre, Phase II Master Protocol Evaluating Different Booster Strategies in Individuals Already Vaccinated Against SARS-CoV-2.

This is a randomised controlled, adaptive, evaluator-blinded multicentre Phase II protocol evaluating immunogenicity and reactogenicity of different booster strategies in individuals 75 years and older already vaccinated against SARS-CoV-2. This trial foresees testing of different vaccines as a third booster dose (homologous and heterologous) for comparative assessment of their immunogenicity and safety against SARS-CoV-2 and SARS-CoV-2 variants in aged population, a usually neglected population. Different vaccines and extended follow-up visits can be added by means of amendments to this trial. As stated in the master protocol, this trial implements a specific safety monitoring strategy for a control group as implemented in the EU-COVAT subprotocol with the EudraCT no.: 2021-004889-35, a separate sub-protocol embedded within the EU-COVAT master protocol (see below). This control group is used for exploratory comparison.

Vaccines used in this trial will be those already marketed and in their commercial presentation. The sample size planned is adequate for a precise enough estimation of the immune response after a 3rd vaccination dose. Also, it will provide adequate power for comparison in GMT (Geometric mean titre values) between the two randomised treatment arms in aged patients, e.g., comparison of homologous versus heterologous boosting strategies depending on the initial vaccination.

Demonstration of equivalent immune response after heterologous boosting, in comparison with the homologous approach, will facilitate vaccination programs when vaccine availability is an issue.

15 Assignment of trial subjects to treatment groups

According to section 4.7.5 of the accompanying master protocol:

